7.4.1. Drug-Induced Liver Injury

Events of potential hepatic injury will be reviewed and adjudicated by the Hepatic Safety Adjudication Committee (HSAC) as described in [Section 16.11](#). The specific criteria for identification and adjudication of potential hepatic injury events are described in the HSAC charter.

[figure not shown]
Liver biochemistries will be evaluated to assess biochemical triggers that will prompt an immediate reevaluation of subjects. Thus, these assessments will be performed at:

- Each protocol-specified visit
- Unscheduled visits in the event of signs or symptoms of potential hepatic injury, decompensation, or if laboratory alerts have been triggered

It is important that the laboratory assessments be completed as required and that the central laboratory be used for assessments whenever possible. If a subject cannot return to the clinic for a scheduled or unscheduled visit, or there is an event that triggers a need for an immediate assessment, the use of a local laboratory is required. In these cases, the Investigator will obtain the laboratory results and the laboratory normal ranges. All local laboratory data, including the reference ranges, are to be collected and entered in the eCRF within 2 days of receiving the results. For guidance on alternative processes under which subjects may complete the protocol-specified assessments under COVID-19 restrictions refer to [Section 10](#). Local laboratory visits in conjunction with remote (telemedicine) visits are specifically encouraged in lieu of on-site visits where subject's safety is of concern (eg, adverse event monitoring).

The process for assessing subjects using specific criteria is presented in [Figure 2](#), and the specific threshold(s) for each laboratory analyte to trigger mandatory repeat testing and potentially a complete subject evaluation (depending on the repeat result) are summarized in [Table 2](#).

Figure 2: Potential DILI Management Algorithm for Study 747-303

ALP = alkaline phosphatase; ALT = alanine aminotransferase; BL = baseline; eCRF = Electronic Case Report Form; INR = international normalized ratio; IP = Investigational Product; PK = pharmacokinetic; TB = total bilirubin; ULN = upper limit of normal.

Laboratory assessments include: ALT, ALP, direct and total bilirubin, INR.

^a Signs and symptoms of hepatic injury include severe fatigue, nausea, vomiting, right upper quadrant pain, fever, rash, and eosinophilia.

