^b Lower severity treatment-emergent threshold criteria include the following from Table 2:

- 1) In subjects with normal/near normal ALT at baseline and treatment-emergent ALT $\geq 5x$ ULN, TB normal, or with Gilbert's: no change in BL TB
- 2) In subjects with elevated ALT at baseline and treatment-emergent ALT $\geq 3x$ BL or ≥ 300 U/L, whichever occurs first, TB normal, or with Gilbert's: no change from BL TB
- 3) In subjects with baseline ALP \leq ULN and treatment-emergent ALP $\geq 2x$ BL and $>$ ULN but < 250 U/L
- 4) In subjects with baseline ALP $>$ ULN and treatment-emergent ALP $\geq 2x$ BL but < 300 U/L

^c If a subject is unable to return to the site for repeat test, the subject MUST have repeat (or any safety) laboratory tests performed at a local laboratory. All local laboratory results, including reference ranges, should be entered in the eCRF within 2 days of receiving results.

^d PK sampling must be conducted within 7 days of IP interruption; close monitoring including physical exams and repeat laboratory testing should occur as often as deemed appropriate by the Investigator. In subjects with signs or symptoms of hepatic injury, the Medical Monitor should be promptly contacted upon awareness for consultation regarding management of the subject.

Table 2: Liver Laboratory Criteria for Monitoring for Potential Hepatic Injury

Baseline	Treatment Emergent	Signs and Symptoms of Hepatic Injury ^a	Action
ALT Normal/Near Normal^b	ALT $\geq 5x$ ULN TB normal Gilbert's ^c : no change in BL TB	No	
 Repeat laboratory testing including CPK within 2-4 days
	ALT $\geq 3x$ ULN Regardless of TB or DB	Yes	Interrupt 
 Repeat laboratory testing including CPK within 2-4 days Collect PK sample within 7 days
	ALT $\geq 8x$ ULN Regardless of TB or DB	No	Interrupt 
 Repeat laboratory testing including CPK within 2-4 days Collect PK sample within 7 days
	ALT $\geq 3x$ ULN TB $\geq 2x$ ULN Gilbert's ^c : DB $\geq 2x$ ULN or INR >1.5	No	Interrupt 
 Repeat laboratory testing including CPK within 2-4 days Collect PK sample within 7 days
ALT Elevated^b	ALT $\geq 3x$ BL or ≥ 300 U/L, whichever occurs first TB normal Gilbert's ^c : no change from BL TB	No	
 Repeat laboratory testing including CPK within 2-4 days

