	ALT $\geq 2x$ BL or ≥ 300 U/L, whichever occurs first Regardless of TB or DB	Yes	Interrupt 
 Repeat laboratory testing including CPK within 2-4 days Collect PK sample within 7 days
	ALT $\geq 5x$ BL or ≥ 500 U/L, whichever occurs first Regardless of TB or DB	No	Interrupt 
 Repeat laboratory testing including CPK within 2-4 days Collect PK sample within 7 days
	ALT $\geq 2x$ BL or ≥ 300 U/L, whichever occurs first TB $\geq 2x$ ULN Gilbert's ^c : DB $>2x$ ULN or INR >1.5	No	Interrupt 
 Repeat laboratory testing including CPK within 2-4 days Collect PK sample within 7 days
TB (>1.5 mg/dL exclusion criterion 747-303)	TB ≥ 2.0 mg/dL and DB $>30\%$ of TB	Yes/No	Interrupt 
 Repeat laboratory testing including CPK within 2-4 days Collect PK sample within 7 days

Table 2: Liver Laboratory Criteria for Monitoring for Potential Hepatic Injury (Continued)

Baseline	Treatment Emergent	Signs and Symptoms of Hepatic Injury ^a	Action
ALP ≤ULN ^d	ALP ≥2x BL and >ULN	No	
If ALP <250 U/L, then:
 
 Repeat laboratory testing including CPK within 2-4 days 
If ALP ≥250 U/L, then:
 
Interrupt
 
 Repeat laboratory testing including CPK within 2-4 days Collect PK sample within 7 days
		Yes	
Interrupt
 
 Repeat laboratory testing including CPK within 2-4 days Collect PK sample within 7 days
ALP >ULN ^d	ALP ≥2x BL or >300 U/L, whichever occurs first	No	
If ALP <300 U/L, then:
 
 Repeat laboratory testing including CPK within 2-4 days 
If ALP ≥300 U/L, then:
 
Interrupt
 
 Repeat laboratory testing including CPK within 2-4 days Collect PK sample within 7 days
		Yes	
Interrupt
 
 Repeat laboratory testing including CPK within 2-4 days Collect PK sample within 7 days

ALP = alkaline phosphatase; ALT = alanine aminotransferase; BL = baseline; DB = direct bilirubin; CPK = creatine phosphokinase; DILI = drug-induced liver injury; INR = international normalized ratio; NASH = nonalcoholic steatohepatitis; OCA = obeticholic acid; PK = pharmacokinetic; TB = total bilirubin; ULN = upper limit of normal

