^a Signs and symptoms of hepatic injury include severe fatigue, nausea, vomiting, right upper quadrant pain, fever, rash, and eosinophilia.

^b Baseline ALT is defined as an average of all pre-treatment values from Screening and Day 1. Elevated Baseline defined as ALT ≥1.5x ULN. ALT decreases are common within the first 3-6 months of treatment in NASH subjects receiving OCA. If there is a decrease in ALT for all lab draws through the Month 6 Visit, then a new baseline should be established for subsequent DILI determination, based on the average ALT from the Month 3 and Month 6 Visits.

^c A subject will be considered to have Gilbert's syndrome if it was established at baseline and documented in the subject's medical history.

^d Baseline ALP is defined as an average of all pre-treatment values from Screening and Day 1. Modest ALP increases (<50%) from baseline within the first 3 months of treatment are common in NASH subjects receiving OCA and represent an expected pharmacodynamic effect. If there is an increase in ALP through the Month 6 Visit, then a new baseline should be established for subsequent DILI determination, based on the average ALP from the Month 3 and Month 6 Visits.

If any subject meets the triggering threshold limits indicated in [Table 2](#) and experiences signs or symptoms of hepatic injury (severe fatigue, nausea, vomiting, right upper quadrant pain, fever, rash, eosinophilia) investigational product should be immediately interrupted (see [Section 7.7](#) for dosing modifications).

If no signs or symptoms of hepatic injury are present, but liver biochemistries are above the triggering threshold limits, the subject should either interrupt investigational product or laboratory assessments including creatine phosphokinase (CPK) should be repeated within 2-4 days according to the threshold limits specified in [Table 2](#). If a repeat laboratory test cannot be performed within 7 days of receiving results, the subject should be instructed to interrupt investigational product until repeat laboratory test results have been reviewed.

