Subjects should, wherever possible, come back to the site. It may be difficult for subjects who are distant from their study site to return to the site promptly. Such subjects must have repeat (or

any safety) laboratory tests performed at a local laboratory, but normal laboratory ranges and the results should be made available to the Investigator. All local laboratory data, including reference ranges, should be entered in the eCRF within 2 days of receiving the results. The original or copies should be retained at the site as the source documents. For guidance on alternative processes under which subjects may complete the protocol-specified assessments under COVID-19 restrictions refer to [Section 10](#).

It should be noted that it is difficult to recognize every potential marker of hepatic deterioration. There is no substitute for good medical judgment. Investigators will be reminded to be cautious and mindful in their evaluation of subjects' symptoms, signs, and laboratory results. However, for example, a single abnormal laboratory analyte result may be artefactual or may clearly be explained for a particular subject as due to pre-existing conditions or circumstances unrelated to their liver function or the study; accordingly, Investigators may be allowed to implement an alternate follow-up procedure, based on their medical judgement, but only after documented consultation and agreement with the Sponsor's Medical Monitor.

Specific aspects of the Potential DILI Management Algorithm may be adjusted, in which case specific guidelines will be provided to the sites for implementation.

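### Table 2 and its SAP copy give no action for a symptom-free subject with an intermediate ALT rise and mildly raised bilirubin

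*Protocol*

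**What the plan says.** Protocol 7.4.1 places the process in Figure 2 and the thresholds in Table 2, which are there "to trigger mandatory repeat testing and potentially a complete subject evaluation". SAP Appendix D copies the table. For a subject without signs or symptoms, the ALT and bilirubin rows are:

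- **Normal or near-normal baseline ALT, repeat in 2-4 days:** ALT >=5x ULN with normal TB. Figure 2 footnote b restates this as "In subjects with normal/near normal ALT at baseline and treatment-emergent ALT $\geq 5x$ ULN, TB normal". For Gilbert's subjects the condition is no change from baseline TB.
- **Normal or near-normal baseline ALT, interrupt:** ALT >=8x ULN at any bilirubin; or ALT >=3x ULN with TB >=2x ULN (Gilbert's: "DB $\geq 2x$ ULN or INR >1.5").
- **Elevated baseline ALT, repeat in 2-4 days:** ALT >=3x baseline or >=300 U/L, with the same bilirubin condition. The table footnote gives "Elevated Baseline defined as ALT ≥1.5x ULN".
- **Elevated baseline ALT, interrupt:** ALT >=5x baseline or >=500 U/L at any bilirubin; or ALT >=2x baseline or >=300 U/L with TB >=2x ULN (Gilbert's: "DB $>2x$ ULN or INR >1.5").
- **Bilirubin row, interrupt with or without symptoms:** "TB ≥ 2.0 mg/dL and DB" above 30% of TB.

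The text after the table says that, for symptom-free subjects above the limits, either the product is interrupted or tests "should be repeated within 2-4 days according to the threshold limits specified in" Table 2.

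**The concern.** Both symptom-free repeat rows stop applying as soon as TB leaves the normal range, and the combined ALT-bilirubin interruption rows start only at TB 2x ULN. Between the two, the table is silent for an ALT rise that on its own would require a repeat within days.

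ALT and bilirubin rising together is the pattern these rows exist to catch. After Month 18 scheduled visits are six months apart (Protocol 7.1), so the triggered repeat is the specific short-interval check. Protocol 5.5 reports 9 hepatic decompensation SUSARs in NASH trials and more frequent serious hepatic events on OCA 25 mg.

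Some subjects may start inside the bilirubin band. Exclusion criterion 6 admits subjects without Gilbert's syndrome up to TB 1.5 mg/dL. If the laboratory ULN is 1.25 mg/dL, a subject who enters at 1.4 and stays there never has normal TB, and the repeat row can never apply to that subject.

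**Working it through.** The plan gives no figure to reproduce. The check is whether the rows cover every combination of ALT and bilirubin.

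**Inputs.** The rows are those of Table 2, for a subject with no symptoms, INR <=1.5 and no ALP trigger. The protocol states no laboratory ULN, so ULNs are assumed. SAP 10.5.4 uses ALT 30 U/L, TB 1.25 mg/dL and DB 0.3 mg/dL for its analyses; other values are shown as a range.

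**ALT band in which only the repeat row could apply.**

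- Normal or near-normal baseline: 5 x ULN <= ALT < 8 x ULN. This is 150-239 U/L at ULN 30, 200-319 at ULN 40 and 250-399 at ULN 50.
- Elevated baseline (BL): min(3 x BL, 300) <= ALT < min(5 x BL, 500). BL 45 gives 135-224 U/L; BL 60 gives 180-299; BL 80 gives 240-399; BL 100-200 gives 300-499.

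**TB band with no row, subjects without Gilbert's.** The lower edge is just above ULN. The upper edge is 2.0 mg/dL if DB is >30% of TB (bilirubin row), otherwise 2 x ULN (combined row).

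| TB ULN (assumed) | No row, any DB fraction | Extends to, if DB <=30% of TB |
|---|---|---|
| 1.0 | 1.01-1.99 | no extension (2 x 1.0 = 2.0) |
| 1.25 | 1.26-1.99 | 2.49 (2 x 1.25 = 2.5) |
| 1.5 | 1.51-1.99 | 2.99 (2 x 1.5 = 3.0) |

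**Worked case.** Baseline ALT 30, ALT 210 U/L (7 x 30), TB ULN 1.25:

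| TB (mg/dL) | Row met |
|---|---|
| 1.2, 1.25 | repeat in 2-4 days |
| 1.3, 1.5, 1.8, 1.99 | none |
| 2.0, 2.4, 2.49 | interrupt if DB is 40% of TB; none if 20% |
| 2.5 | interrupt |

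Baseline ALT 80 with ALT 300 U/L gives the same pattern.

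**Gilbert's case.** Baseline TB 1.8, DB ULN 0.3 (so 2 x ULN = 0.6), ALT 180 U/L (6 x 30). At TB 1.8 the repeat row applies. At TB/DB of 1.9/0.3, 2.2/0.4, 2.6/0.5 and 3.0/0.59 no row applies. At 3.0/0.60 the normal-baseline row interrupts, but with an elevated baseline (BL 80, ALT 300) no row applies, because that criterion uses > where the other uses >=. At 2.0/0.61 (30.5%) the bilirubin row interrupts.

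**INR wording.** The clause on INR >1.5 follows the Gilbert's condition, and it is unclear whether it applies to everyone. At ALT 180, TB 1.5 and INR 1.6, reading it as general gives interruption; reading it as Gilbert's only gives no row. Restricting the point to INR <=1.5 makes it hold either way.

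**Does a new row close the gap?** Within the ALT band, normal TB, TB >ULN to <2x ULN, and TB >=2x ULN cover every value. For Gilbert's, unchanged TB, changed TB with DB <2x ULN, and DB >=2x ULN do the same once the two DB criteria are aligned.

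**The case against.** The strongest reply is that Figure 2, not Table 2, governs the process, and its drawing is not available here. Appendix F says the revised figure asks whether the threshold met belongs to a lower-severity class. Footnote b confines that class, for ALT, to normal TB or unchanged TB in Gilbert's. It is natural to infer that the same ALT with raised TB goes to interruption. The text after Table 2 also offers only two outcomes for symptom-free subjects above the limits, interrupt or repeat, and Table 4 likewise has no option of doing nothing. If ALT >=5x ULN is itself the trigger and normal TB only selects the milder action, these subjects get at least a repeat.

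This stands as far as it goes. A reader might infer from the table that the trial's mandated response weakens as bilirubin rises, or that these subjects are left unmanaged. The documents do not support that, because Figure 2 may interrupt them and the text can be read as requiring a repeat. It does not supply the missing row: both the text and Table 4 send the reader back to the Table 2 limits, and Appendix D carries no figure.

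The more dangerous combinations are caught, since TB >=2x ULN with a lower ALT, TB >=2.0 mg/dL with DB >30% of TB, and high ALT alone all interrupt. Other safeguards exist: prompt evaluation (7.4), medical judgment (7.4.1), interruption at any time for safety (7.7), follow-up until values return to normal or baseline (15.1.11) and follow-up of abnormal laboratory values (15.2.6). None sets a 2-4 day limit. Table 4 also discontinues product for related events of Grade 3 or above, but the grading tables are not in the text available, so whether that covers these ALT values cannot be checked.

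**Conclusion.** The omission is real and worth correcting. Table 2 and SAP Appendix D state no action for symptom-free subjects with INR <=1.5, no ALP trigger, intermediate ALT, and TB above ULN but below 2x ULN and not caught by the bilirubin row. Gilbert's subjects whose TB has changed and whose DB is below its 2x ULN trigger are in the same position, unless the bilirubin row catches them. The gap appears at every ULN tried; only its edges move. The conclusion is about what the table says, not about what sites do.

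A reader might also take this as a matter of subject management alone. That is not quite so. SAP 10.5.4 plans a count of subjects meeting the stopping criteria by reference to Appendix D. If interruption is the intended action for this group, that count would miss them. The separate SAP 10.5.4 trigger of ALT >=5x ULN in subjects with normal baseline biochemistry has no bilirubin condition and is unaffected; it also suggests the gap was not intended.

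The documents give no basis for estimating how many subjects fall in the gap.

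**What to change.** First confirm what Figure 2 does with these subjects. Then:

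- Add one row for each baseline ALT stratum to Table 2 and SAP Appendix D: intermediate ALT with TB >ULN to <2x ULN (Gilbert's: TB changed from baseline and DB <2x ULN). The action is at minimum repeat tests with CPK within 2-4 days, or interruption if Figure 2 already directs it.
- Make Figure 2 footnote b consistent with the new row.
- State that stricter rows take precedence: the bilirubin row, the INR criterion and the ALT-only interruption rows.
- Change the elevated-baseline Gilbert's criterion to DB >=2x ULN, to match the normal-baseline row.

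The cost is some wording in one table, one footnote and one appendix, plus a few extra repeat tests or interruptions. A protocol revision needs ethics review across up to 400 sites, so the change can wait for the next amendment. It could also go out sooner as site guidance, since Protocol 7.4.1 provides that "Specific aspects of the Potential DILI Management Algorithm may be adjusted".

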7.4. Monitoring and Management of Potential Hepatic Injury and/or Decompensation

AEs, signs and symptoms of potential hepatic injury or decompensation, and laboratory values will be reviewed at regular intervals as described in the following subsections ([Section 7.4.1](#) to [Section 7.4.2.1](#)). Based on the assessments of signs and symptoms of hepatic injury ([Appendix C](#)) and liver biochemistry, investigational product will be continued, interrupted, or discontinued per criteria discussed in [Section 7.7](#), and close monitoring procedures will be implemented (refer to [Section 7.4.3](#)).

In the event of a potential hepatic injury, the subject should be promptly brought into the clinic to undergo a complete evaluation including laboratory assessments, physical examinations, and review of signs and symptoms of potential hepatic injury or decompensation.

The Investigator will educate each subject about recognizing the signs and symptoms of hepatic injury or decompensation and instruct each subject to contact the study site to report the onset of any of the signs and symptoms during the study. The Investigator will instruct subjects to seek immediate medical attention if they experience signs or symptoms of hepatic injury or decompensation.

[Appendix C](#) provides guidance for review of signs and symptoms of hepatic injury or decompensation described below to be evaluated at each study visit, or as frequently as needed per Investigator's discretion.

Signs and Symptoms of Hepatic Injury or Decompensation:

- Specific signs and symptoms of liver impairment: yellowing of the skin or the whites of eyes, pale-colored stools, urine color change from pale to deep amber [dark], severe fatigue, right upper quadrant pain, rash, eosinophilia
- More general signs and symptoms of ascites and encephalopathy: swelling of the legs or abdomen, confusion, or abrupt abnormal behavior
- Non-specific signs and symptoms of impaired health: nausea, vomiting, abdominal pain, diarrhea, weight loss, fever and chills, worsening or new fatigue, weakness, loss of appetite
- Significant intercurrent illnesses such as gastroenteritis may exacerbate hepatic injury or decompensation (eg, established severe abdominal pain, vomiting, and diarrhea) and should be an indication for prompt investigational product interruption and complete subject evaluation

Other Symptoms:

- Worsening or new pruritus
- Decreased urine output, dizziness, or lethargy

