Healthcare Provider (HCP) Interactions will be reported:

- Visits to primary HCP or referral to any specialist for any new symptoms (other than ongoing care for stable comorbidities)
- New medications or changes to current medications prescribed from HCP or any new over the counter medications or herbal supplements (refer to [Section 9.3](#))
- Laboratory procedures or assessments performed by an HCP

Signs and symptoms of potential hepatic injury or decompensation should be followed by (1) evaluation of liver biochemistry for potential drug-induced liver injury (DILI) ([Section 7.4.1](#)), (2) assessment for disease progression to cirrhosis ([Section 7.4.2](#)), (3) triggering of investigational product interruption or discontinuation per criteria ([Section 7.7](#)), (4) documentation in the AE eCRF or the SAE eCRFs ([Section 15.1.5](#) and [Section 15.1.6](#)), and (5) contact with the medical monitor.

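### The sign list that triggers immediate interruption omits yellow skin or eyes, pale stools and dark urine, and Section 7.4.1 states it as a closed list

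*Protocol*

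**What the plan says.** Protocol Section 7.4 groups the signs to be reviewed at visits, and Appendix C repeats the groups. The first group opens with "Specific signs and symptoms of liver impairment: yellowing of the skin or the whites of eyes, pale-colored stools, urine color change" and continues with rash, eosinophilia, right-sided upper abdominal pain and severe fatigue, which makes seven specific signs. A separate group opens with "Non-specific signs and symptoms of impaired health: nausea, vomiting, abdominal pain, diarrhea, weight loss, fever and chills".

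Section 7.4 says that, on the basis of the Appendix C signs and liver biochemistry, "investigational product will be continued, interrupted, or discontinued per criteria discussed in" Section 7.7. It also says that signs should be followed by biochemistry, assessment for cirrhosis, "triggering of investigational product interruption or discontinuation per criteria" in Section 7.7, documentation, and contact with the medical monitor.

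The operative rule is in Section 7.4.1: a subject who meets a Table 2 threshold and "experiences signs or symptoms of hepatic injury (severe fatigue, nausea, vomiting, right upper quadrant pain, fever, rash, eosinophilia) investigational product should be immediately interrupted". Table 2 has a Yes/No column for signs and symptoms, keyed to footnote a: "Signs and symptoms of hepatic injury include severe fatigue, nausea, vomiting, right upper quadrant pain, fever, rash, and eosinophilia". Figure 2 footnote a, Table 4 footnote d (in Section 7.7) and SAP Appendix D footnote a carry the same list.

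Without symptoms, some thresholds call only for a repeat test. Figure 2 footnote b gathers them: "Lower severity treatment-emergent threshold criteria include the following from Table 2". The repeat is due in 2 to 4 days, and there is a limit: "If a repeat laboratory test cannot be performed within 7 days of receiving results, the subject should be instructed to interrupt investigational product".

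**The concern.** The review list and the list that drives dosing do not match. Subjects are told to seek immediate medical attention for yellow eyes, pale stools or dark urine (Appendix C), and sites ask about them, but the sentence ordering interruption does not name them. Section 7.4 sends drug action to Section 7.7, and Table 4 there uses the same short list, so the cross-reference does not settle the matter.

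Read literally, nausea with ALT at 3× ULN means immediate interruption, while dark urine at the same ALT does not. Two sites could handle the same subject differently. This matters because Section 5.5 reports serious hepatic events more often on OCA 25 mg than on OCA 10 mg or placebo. SAP Section 10.5.4 also tabulates the subjects who met the stopping criteria, by criterion, so uneven readings could reach a safety table.

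**Working it through.** **Step 1. Compare the lists.** Section 7.4 has 7 specific signs and the trigger list has 7 items. In common: severe fatigue, right-sided upper abdominal pain, rash, eosinophilia (4). Specific but not on the trigger list: yellow skin or eyes, pale stools, dark urine (7 − 4 = 3). On the trigger list but from the non-specific group: nausea, vomiting, fever (7 − 4 = 3).

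**Step 2. Open or closed?** The four footnotes introduce the items with *include*. The Section 7.4.1 sentence gives them in a bare parenthesis.

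**Step 3. Does the flag change the action?** Read Table 2 row by row with the sign flag switched and no bilirubin row met (BL = baseline):

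| Cell | Baseline | On-treatment value | Yes | No |
|---|---|---|---|---|
| 1 | ALT normal/near normal | 5× to <8× ULN, TB normal | interrupt | repeat |
| 2 | ALT elevated | ≥3× BL or ≥300 U/L, but <5× BL and <500 U/L, TB normal | interrupt | repeat |
| 3 | ALP ≤ULN | ≥2× BL and >ULN, but <250 U/L | interrupt | repeat |
| 4 | ALP >ULN | ≥2× BL, but <300 U/L | interrupt | repeat |
| 5 | ALT normal/near normal | 3× to <5× ULN | interrupt | none listed |
| 6 | ALT elevated | 2× to <3× BL and <300 U/L | interrupt | none listed |

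The flag changes the action in six cells: four repeat-only and two with no Table 2 drug action. Mid-range ALT with raised TB short of a bilirubin row is not counted. That gap affects any subject without symptoms, and Figure 2, which is not shown, may cover it.

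**Step 4. How wide are the cells?** Table 2 gives no ULN values. Assume those in SAP Section 10.5.4: ALT 30 U/L, ALP 120 U/L.

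- Cell 5: 3 × 30 = 90 to <5 × 30 = 150 U/L. Cell 1: 150 to <8 × 30 = 240 U/L. With an assumed ALT ULN of 55, cell 5 is 165 to <275 and cell 1 is 275 to <440 U/L.
- Elevated baseline starts at 1.5 × 30 = 45 U/L. At BL 45, cell 6 is 90 to <135 and cell 2 is 135 to <225 U/L. At BL 100, they are 200 to <300 and 300 to <500 U/L. At BL 150, 2 × 150 = 300, so cell 6 is empty.
- Cell 3: at BL 60, >120 to <250 U/L; at BL 120, 240 to <250 U/L.
- Cell 4: at BL 121, 242 to <300 U/L; at BL 150 it is empty. It therefore exists only for baseline ALP above 120 and below 150 U/L.

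**Step 5. What do the bilirubin rows catch?** TB of at least 2.0 mg/dL with direct bilirubin above 30% of TB interrupts whatever the symptoms. So does TB of at least 2× ULN with ALT at its threshold. Most overt conjugated jaundice is therefore handled without the sign flag. Cells 1 and 2 require normal TB, so they concern mainly pale stools or dark urine.

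**The case against.** The best defence is that the lists are meant to be read together. Four of the five places say *include*, and the column heading uses the same term that Section 7.4 ties to Appendix C, where all three signs appear. Section 7.4.1 closes by saying that not every marker can be recognized and by asking for medical judgment. On that reading a subject with dark urine is already a Yes. This stands as support for an investigator who counts the signs. It does not make the operative sentence clear, and Table 4, to which Section 7.4 defers, uses the short list again.

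A second defence is that the short list may be deliberate. The summary of changes says that the process was revised to agree with published guidance, which cannot be seen here. That is possible, but it does not explain the mismatch with the protocol's own specific group.

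A third is that other safeguards apply, and this largely stands. Potential hepatic injury means a prompt, complete evaluation (Section 7.4). A confirmed elevation means at least 30 days off drug (Section 7.4.1). Drug is stopped if prompt evaluation is impossible (Table 4 footnote a), and the investigator may stop it at any time for safety (Section 7.7).

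A reader might infer that the protocol keeps a jaundiced subject on drug. The documents do not support this: the bilirubin rows make that example nearly empty, and nothing forbids counting jaundice as a sign.

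**Conclusion.** This is an ambiguity in a safety rule, with a small residue. The mismatch of three signs is exact and appears in all five places. The consequence depends on a literal reading of one sentence, for subjects with dark urine or pale stools (rarely jaundice), ALT or ALP in one of the six cells, and no bilirubin row met. In four cells the cost is a delay of about 2 to 4 days, with interruption required if the repeat cannot be done within 7. In cells 5 and 6 the literal reader finds no drug action in Table 2.

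Two stronger inferences should be resisted. *No drug action in Table 2* does not mean no action, since Section 7.4 still calls for biochemistry and medical monitor contact. Nor do the documents show that the non-specific signs were put in to replace the specific ones; they show only that the lists differ. How often any cell would be reached cannot be estimated from the documents, and Figure 2 itself was not available. The point is worth considering as a cheap improvement.

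**What to change.** Add yellowing of the skin or eyes, pale stools and dark urine to the list in Figure 2 footnote a, Table 2 footnote a, the Section 7.4.1 parenthesis, Table 4 footnote d and SAP Appendix D footnote a. Write *including* in the Section 7.4.1 parenthesis so that it agrees with the footnotes. If the sponsor means to leave the three signs out, the protocol should say why.

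No new data are needed, because sites already ask about these signs. The wording needs a protocol revision with ethics approval, at up to 400 sites, so it is best carried in the next amendment. Section 7.4.1 also allows the algorithm to be adjusted through guidelines sent to sites. The SAP summary of stopping criteria would then span two wordings, so the date of change should be recorded.

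The clinical cost is a few more immediate interruptions, each with a possible 30-day minimum before rechallenge. It falls mainly on subjects whose elevation would not have been confirmed, since confirmed elevations already carry at least 30 days off drug. Some would not be hepatic, because Section 7.6.1 and Appendix C also list dark urine as a renal sign. That cost is modest given that nausea alone, with the same laboratory values, already interrupts.
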